4.3.3 Electrocardiograms (ECG)

Twelve-lead triplicate ECG will be performed following the schedule in CSP. The following quantitative ECG measurements will be taken:

- Heart rate (bpm);
- PR interval (msec);
- RR interval (msec);
- QRS interval (msec);
- QT interval (msec);
- Fridericia Corrected QT Interval (QTcF);
- Bazett Corrected QT Interval (QTcB).

An overall Investigator assessment of ECG will be provided (categories "normal", "abnormal, not clinically significant" and "abnormal, clinically significant").

If multiple measurements exist at the same visit/schedule timepoint, average of the quantitative measurement will be used for analysis, and the mode value will be used for category data. In cases of ties, the best interpretation will be used for baseline whereas the worst interpretation will be used for post-baseline measurements.

4.3.4 Vital Signs

The following vital signs will be collected following the schedule in protocol.

- systolic and diastolic blood pressure (mmHg);
- pulse rate (bpm);

In addition to the vital signs, body weight will also be collected and height will be collected at screening.

4.3.5 Physical Examination

A physical examination will be performed and include an assessment of the followings: general appearance, skin, head and neck (including ears, eyes, nose and throat), respiratory, cardiovascular, abdomen, lymph nodes, thyroid, musculo-skeletal (including spine and extremities) and neurological systems. New or aggravated findings when compared to baseline should be recorded as adverse events, so detailed physical examination results will not be collected.

Performance status will be assessed as scheduled in CSP according to ECOG criteria (score 0 to 4).

4.3.6 Other Safety endpoints

Echocardiogram/MUGA, Pulmonary Function Test, Ophthalmologic Assessment, and etc will also be performed.

4.4 Pharmacokinetics

4.4.1 **Drug Concentration**

Venous blood samples will be collected following the schedule in CSP, for quantification of DZD9008 and metabolite (DZ0753). Patients in part B of study will be invited for intense PK sampling (approximately 10-30% of patients) and the remaining for sparse PK to characterize DZD9008 and metabolite pharmacokinetics. The timepoints are specified in CSP.

Concentrations of DZD9008 and metabolite measured on Cycle 1 Day 1 (prior to dosing on Cycle 1 Day 2) will be regarded as single dose component, and concentations measured on Cycle 3 Day 1 (prior to dosing on Cycle 3 Day 2) will be regarded as steady state after multiple dose. All pre-dose concentrations measured after Cycle 1 Day 1 will be considered as trough concentrations.

Drug Substance: DZD9008 Version Number: Final 2.0

Protocol Number: DZ2019E0001 (Part B) Version Date: 16 Nov 2023

4.4.2 **Pharmacokinetic Parameters**

The following PK parameters will be determined where possible from the plasma concentrations of DZD9008 and metabolite (DZ0753), using no-compartmental methods performed using Phoenix WinNonlin (Certara USA, Inc., Version 8.1 or higher):

Table 3 Single Dose Component for Intense PK (Cycle 1 Day 1 in Part B)

Parameters	Definition
AUC _(0-t)	area under the plasma concentration-time curve from time zero to the time of last measurable concentration
$AUC_{(0-24)}$	area under the plasma concentration-time curve from time zero to 24 hours
C_{max}	maximum plasma concentration
t_{max}	time to C _{max}
Metabolite/Parent Ratio for AUC	ratio of AUC between metabolite and DZD9008 after first dose
Metabolite/Parent ratio for C _{max}	ratio of C_{max} between metabolite and DZD9008 after first dose

Table 4 Multiple Dose for Intense PK (Cycle 3 Day 1 in Part B)

Parameters	Definition
$\mathrm{AUC}_{\mathrm{ss}}$	area under the plasma concentration-time curve from time zero to the end of the dosing interval (dosing interval = 24 hours)
$C_{ss,max}$	maximum plasma concentration at steady state
$C_{\mathrm{ss,min}}$	minimum plasma concentration at steady state
$t_{\rm ss,max}$	time to $C_{ss,max}$
$\mathrm{CL}_{\mathrm{ss}}/\mathrm{F}$	apparent plasma clearance at steady state, calculated by dose/AUC $_{\rm ss}$
RAC_{AUC}	extent of accumulation on multiple dosing based on multiple dose $AUC_{ss}/single$ dose $AUC_{(0\text{-}24)}$
RAC_{Cmax}	accumulation in C_{max} on multiple dosing based on multiple dose $C_{\text{ss,max}}/\text{single}$ dose C_{max}
Metabolite/Parent ratio for AUC _{ss}	ratio of AUC _{ss} between metabolite and DZD9008 after multiple dose
$\label{eq:metabolite-parent} Metabolite/Parent \\ ratio for \ C_{ss,max}$	ratio of $C_{ss,max}$ between metabolite and DZD9008 after multiple dose

Protocol Number: DZ2019E0001 (Part B) Version Date: 16 Nov 2023

Additional PK parameters may be determined where appropriate.

The PK analysis will, where possible, be carried out using actual postdose times recorded in the raw data. If actual times are missing, nominal times may be used.

Concentrations are used as supplied by the analytical laboratory for PK analysis. The units of concentration and resulting PK parameters, with amount or concentration in the unit, will be presented as they are received from the analytical laboratory.

C_{max}, C_{ss,max} C_{ss,min}, t_{max} and t_{ss,max} will be obtained directly from the plasma concentration-time profiles.

For multiple peaks, the highest postdose concentration will be reported as C_{max} and $C_{ss,max}$. In the case that multiple peaks are of equal magnitude, the earliest t_{max} and $t_{ss,max}$ will be reported.

AUC values (AUC_(0-t), AUC₍₀₋₂₄₎, AUC_{ss}) will be calculated using the linear trapezoidal rule for increasing concentrations and the logarithmic rule for decreasing concentrations (linear up/log down rule).

Non-compartmental PK parameters will not be derived for the patients with sparse PK sampling. The PK data from these patients will be used in population PK analyses reported outside the CSR.

4.4.2.1 Criteria for Handling Concentrations Below the Limit of Quantification in Pharmacokinetic Analysis

For PK parameter calculation purpose, concentration below the limit of quantification (BLQ) will be handled following the rules below.

- BLQ value prior to administration of the first dose and up to the first measurable concentration will be set as zero.
- Any embedded BLQ value (between 2 quantifiable concentrations), late quantifiable concentration values (following 2 BLQ values in the apparent terminal phase of the profile) and BLQ values following the last quantifiable concentration in a profile will be set to missing for the purposes of PK analysis unless there is a scientific rationale not to do so which will be documented in the PK Analysis Notes/handover document.
- For single dose part of the study, if a predose concentration is missing for a patient, this will be set to zero by default.

4.4.2.2 Calculation of Area Under the Concentration-time Curve

• The minimum requirement for the calculation of AUC values will be the inclusion of at least 3 consecutive plasma concentrations above the lower limit of quantification (LLOQ), with at least one of these concentrations following C_{max}/C_{ss,max}.

• For any partial AUC determination (i.e. AUC over a dosing interval), nominal time will generally be used for the end of the interval. Actual times for partial AUC intervals may be used at the discretion of the pharmacokineticist.

4.4.2.3 Anomalous Values

- If a value is considered to be anomalous due to being inconsistent with the expected PK profile, it may be appropriate to exclude this point from the PK analysis. However, the exclusion of data must have strong justification and will be documented in the raw data and the CSR.
- Quantifiable predose concentrations following the first administration of DZD9008 will be considered anomalous and set to missing for PK analysis.
- Embedded BLQ values may be considered anomalous depending on the route of administration and the characteristics of the drug.

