- Higher incidence of dose reduction and interruption occurred at 400 mg cohort was observed as compared to 200 mg and 300 mg cohort, which presumably led to lower clinical efficacy at the 400 mg cohort (ORR 25% at 400 mg). As the doses of 100 mg or above demonstrated clinical activity, and 200 mg or 300 mg is expected to overcome PK variability of DZD9008 to achieve pharmacological relevant exposure required from different subtypes of Exon20ins, thus selecting both 200 mg and 300 mg is appropriate to further evaluate DZD9008 dose optimization for the phase 2 pivotal study.
- DZD9008 elimination half-life is approximately 50 hours following a single dose across the doses investigated, which supports the once daily dosing regimen of DZD9008 in clinical development.

Ethnic sensitivity

 Based on the available data, no obvious difference in safety, PK and anti-tumor efficacy of DZD9008 was observed between Asian and White patients across different regions/countries. Therefore, Dizal believes that the use of same dose and schedule across different regions and countries is appropriate.

Patients enrolled to Part B will receive repeated dosing of DZD9008 at 200 mg or 300 mg once daily. Following review and approval form IEC/IRB and/or local regulatory authority (as applicable) on the optimal RP2D selction, eligible patients can be enrolled into the optimal RP2D cohort. The ongoing patients previously randomized to the suboptimal Part B dose cohort can maintain the same dose level, or shift to receive the optimal RP2D, if judged by the investigator that it is of the best clinical benefit to patients and re-consent is needed (see section 5.1). DZD9008 will be administrated with food as dosing with high fat food in Part A showed limited effect on DZD9008 exposure. Patients with prior therapy may be stratified into subcohorts when data is analyzed.

Patients will receive repeated daily dosing of DZD9008 until disease progression, intolerable AEs, discontinuation criteria have met or withdrawal of consent.

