3 hours	X						X						
4 hours	X						X						
6 hours	X						X						
8 hours	X						X						
10 hours	X						X						
12 hours	X						X						
24 hours		X						X					
48 hours			X						X				
72 hours				X						X			
120 hours					X						X		
168 hours						X						X	

Note: The treatment date and sample collection time for each period might change upon emergent human PK data.

- a. A 30 min window is allowed for pre-dose sampling.
- b. A 5 min window is allowed for samples taken at 0.5 hour and 1 hour;
- c. A 10 min window for samples taken at 2-10 hours;
- d. A 1 hour window for samples taken at 12 hours and 24 hours,
- e. A 2 hour window for samples taken at 48 hours, 72 hours, 120 hours and 168 hours.

Table 7 Blood PK sampling schedule (Part A expansion)

Time relative		Cycle 1	Cycle 2	Cycle 3, 4	
to dose	D1	D8	D15	D1	D1
Pre-dose	X	X	X	X	X
0.5 hour	X			X	
1 hour	X			X	
2 hours	X			X	
3 hours	X			X	
4 hours	X			X	
6 hours	X			X	

Time relative		Cycle 1	Cycle 2	Cycle 3, 4	
to dose	D1	D8	D15	D1	D1
8 hours	X			X	
10 hours	X			X	
12 hours	X			X	
24 hours	X (prior to next dose)			X (prior to next dose)	

Note: The treatment date and sample collection time for each period might change upon emergent human PK data.

- a. A 30 min window is allowed for pre-dose sampling.
- b. A 5 min window is allowed for samples taken at 0.5 hour and 1 hour;
- c. A 10 min window for samples taken at 2-10 hours;
- d. A 1 hour window for samples taken at 12 hours and 24 hours.

 Table 8
 Blood collection for intense PK (Part B extension)

Time	Cy	Cycle 1			Cycle 3	Cycle 5	Cycle 7	Cycle 9	Cycle 11
relative to dose	D1	D8	D15	D1	D1	D1	D1	D1	D1
Pre-dose ^a	X	X	X	X	X	X	X	X	X
1 hour ^b	X				X				
2 hours ^c	X				X				
3 hours ^c	X				X				
4 hours ^c	X				X				
6 hours ^c	X				X				
8 hours ^c	X				X				
24 hours ^d	X (prior to next dose)				X (prior to next dose)				

- a. A 30 min window is allowed for pre-dose sampling.
- b. A ± 5 min window is allowed for samples taken at 1 hour;
- c. $A \pm 10$ min window for samples taken at 2-8 hours;
- d. A ± 1 hour window for samples taken at 24 hours.

Note: When the timing of a PK or safety laboratory blood sample coincides with the timing of ECG measurements, the ECG will be completed before the collection of the blood samples.

Date: July 24,2023

Table 9 Blood collection for sparse PK (Part B extension)

Time	Cycle 1		Cycle 2	Cycle 3	Cycle 5	Cycle 7	Cycle 9	Cycle 11	
relative to dose	D1	D8	D15	D1	D1	D1	D1	D1	D1
Pre-dose ^a	X	X	X	X	X	X	X	X	X

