5.8.1 Summary of Drug Concentration

Drug concentration data will be analyzed and reported in PKS.

Concentrations of DZD9008 in plasma following single dose and multiple dose (steady state) will be summarized separately by nominal timepoint within each treatment group for subjects with intense PK in PKS. The concentration collected at the overlapped timepoints between intense and sparse PK will be summarized by nominal timepoint and treatment group in PKS. Extra measurements (such as unscheduled or repeat assessments) will not be included in the summary tables, but will be included in individual data listings.

The following summary statistics will be provided for concentration in the summary tables:

- Number of observations
- Number of observations below Lower Limit of Quantification (LLOQ)
- Arithmetic mean calculated using untransformed data
- Standard Deviation (SD) calculated using untransformed data
- The geometric mean (calculated as $\exp[\mu]$, where μ is the mean of the data on a logarithmic scale)
- Geometric coefficient of variation (CV, calculated as $100\sqrt{[\exp(s2)-1]}$, where s is the standard deviation of the data on a log scale)
- Geometric mean \pm SD (calculated as exp[$\mu\pm$ s])

Median

- Minimum
- Maximum

The drug concentration will also be displayed graphically, including the intense PK samples and the trough (pre-dose) concentration from all patients. Plasma concentration will be plotted (on the linear and log-scale) versus time for each individual patient. The geometric mean will also be plotted versus the nominal timepoint, grouped by treatment. And the error bar for geometric mean \pm SD will be added if appropriate.

All drug concentration data collected will be presented in the individual data listing, including the data excluded from analysis and the extra measurements (such as unscheduled or repeat assessments).

Concentration of metabolite (DZ0753) will also be analyzed and reported using the same method.

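### SAP 4.4.2.3 sets quantifiable pre-dose concentrations after the first dose to missing: it targets the wrong samples, contradicts SAP 4.4.1 and removes the time-zero point of AUCss

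*SAP*

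**What the plan says.** The second bullet of SAP 4.4.2.3 (Anomalous Values) reads: "Quantifiable predose concentrations following the first administration of DZD9008 will be considered anomalous and set to missing for PK analysis". It is mandatory and carries no exception. The bullet before it, on values that do not fit the expected profile, is discretionary and asks for strong justification.

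SAP 4.4.1 treats the same samples differently: "All pre-dose concentrations measured after Cycle 1 Day 1 will be considered as trough concentrations". SAP 5.8.1 then plans plots "including the intense PK samples and the trough (pre-dose) concentration from all patients".

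SAP Table 4 defines AUCss at Cycle 3 Day 1 as: "area under the plasma concentration-time curve from time zero to the end of the dosing interval (dosing interval = 24 hours". Time zero of that interval is the Cycle 3 Day 1 pre-dose sample.

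SAP 4.4.2.1 has one rule for a missing pre-dose value: it is set to zero, in the single-dose part only. Nothing is said for steady state.

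Protocol 5.1.4 gives the kinetics: "DZD9008 elimination half-life is approximately 50 hours following a single dose across the doses investigated".

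**The concern.** A measurable drug level before a patient's first dose is an anomaly. A measurable level before any later daily dose, with a half-life twice the dosing interval, is what the drug should produce. The sentence puts the anomaly on the wrong side of the first administration.

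Two things follow. The samples that SAP 4.4.1 calls troughs become values to discard. And the value the sentence presumably aims at, a quantifiable Cycle 1 Day 1 pre-dose concentration, gets no explicit rule, because SAP 4.4.2.1 deals there only with values below the quantification limit.

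PK is a secondary objective of Part B, and the steady-state parameters are listed outputs. If the rule is followed, AUCss has no defined start. If it is ignored, the analysis departs from its own SAP.

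**Working it through.** **Which samples the rule reaches.** Protocol Tables 8 and 9 schedule pre-dose samples at nine visits: Cycle 1 Days 1, 8 and 15, and Day 1 of Cycles 2, 3, 5, 7, 9 and 11.

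- Intense schedule: 9 pre-dose + 2 × 7 post-dose (1, 2, 3, 4, 6, 8 and 24 h on Cycle 1 Day 1 and Cycle 3 Day 1) = 23 samples.
- Sparse schedule: 9 pre-dose + 2 × 2 post-dose (4 and 8 h on the same two days) = 13 samples.
- Pre-dose after the first dose: 9 − 1 = 8 in either schedule.

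**Which of these enter a listed parameter.** SAP Tables 3 and 4 use only the Cycle 1 Day 1 and Cycle 3 Day 1 profiles, and SAP 4.4.2 derives no non-compartmental parameters for sparse-PK patients. So one of the eight matters: Cycle 3 Day 1 pre-dose, in the intense-PK subset (about 10 to 30% of patients). The Cycle 1 Day 1 pre-dose sample precedes the first dose, so AUC(0-24) is not touched.

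**Size, by hand.** If AUCss is taken from the first remaining sample at 1 h, one hour of 24 is lost. For a flat profile that is 1/24 = 4.2%. Protocol 2.3.5 describes the steady-state profile as flat. The first hour lies near the trough, so the loss should be slightly below 4.2%.

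**Size, by model.** The plan gives no figure to reproduce. The illustration is a one-compartment oral model with unit dose/volume and superposition over n daily doses:

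C(t) = Σ (j = 0 to n − 1) ka/(ka − k) × [exp(−k(t + 24j)) − exp(−ka(t + 24j))], with k = ln 2 / half-life.

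Cycle 3 Day 1 is dose 21 + 21 + 1 = 43. Sampling is at 0, 1, 2, 3, 4, 6, 8 and 24 h, with AUC by linear up/log down as in SAP 4.4.2. Half-life is 50 h from the protocol, varied over 40 to 60 h by assumption. The absorption rate ka (0.3, 0.6 and 1.2 per h) is also assumed, because tmax is blacked out. Only the Cycle 3 Day 1 pre-dose value is removed.

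| Half-life 50 h, ka | AUC(0-24) | AUCss, full | RAC(AUC) | Loss of observed AUCss | Css,min, reduced/full |
|---|---|---|---|---|---|
| 0.3 | 17.46 | 71.69 | 4.11 | 3.9% | 1.000 |
| 0.6 | 19.08 | 72.02 | 3.77 | 3.9% | 1.000 |
| 1.2 | 19.71 | 72.03 | 3.65 | 4.0% | 1.000 |

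Worked through for ka = 0.6:

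- AUCss becomes 72.02 × (1 − 0.039) = 69.21.
- RAC(AUC) becomes 69.21/19.08 = 3.63.
- CLss/F, being dose/AUCss, is multiplied by 1/(1 − 0.039) = 1.041.

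Over all nine combinations of half-life and ka, the AUCss loss is 3.8 to 4.0%, so CLss/F rises by 1/0.962 − 1 = 4.0% to 1/0.960 − 1 = 4.2%. Css,min does not move, because the 24-hour value stands in for the pre-dose value. RAC(Cmax) uses no pre-dose value unless the peak falls there.

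**The case against.** The sponsor can argue that the sentence was meant for the pre-dose sample belonging to the first-dose profile, where a quantifiable value is anomalous. That is plausible, but the words do not say it.

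Scope is the stronger defence. The rule sits under Pharmacokinetic Parameters and is limited to PK analysis. Concentration summaries and trough plots come under SAP 5.8.1, which also lists excluded data. So it cannot be said that the troughs disappear from the report, and seven of the eight affected samples feed no listed parameter. This stands, although the SAP does not define where PK analysis ends.

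There are safeguards too. SAP 5.8 has a clinical pharmacologist confirm the exclusions it lists, and discarding every trough would probably be noticed. PK is summarised descriptively and has no bearing on the ORR test. These points lower the stakes but do not repair a mandatory rule that conflicts with SAP 4.4.1.

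**Conclusion.** The sentence is wrong as written. It contradicts SAP 4.4.1, misses the sample it should cover, and leaves AUCss without a time-zero value or a stated substitute. With the 24-hour sample kept, the cost is about 4% in each of AUCss (down), CLss/F (up) and RAC(AUC) (down). Css,min is essentially unchanged and first-dose AUC(0-24) is untouched. The 4% assumes that AUCss is then measured from 1 h. It depends little on the assumed half-life and ka, because it is close to one hour out of 24.

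A reader might infer a far larger loss by counting the 24-hour samples as pre-dose, since their entry in Protocol Table 8 begins "X (prior to next dose", and Protocol Table 5 even marks a Part A 24-hour sample as a Day 2 pre-dose draw. On that reading nothing remains after 8 h. In the same model, 67 to 70% of observed AUCss and 65 to 73% of AUC(0-24) would go, and Css,min would be 7 to 32% too high.

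The Part B documents do not support it. Table 8 gives the 24-hour sample its own row and a ±1 hour window, separate from the pre-dose row and its 30-minute window. SAP 4.4.1 assigns it to the profile of the preceding dose: what is "measured on Cycle 1 Day 1 (prior to dosing on Cycle 1 Day 2) will be regarded as single dose component". It places the Cycle 3 samples drawn up to the Day 2 dose in the steady-state profile in the same way. The larger figures show why the text should exclude that reading; they do not measure what the plan does.

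**What to change.** Reword the second bullet of SAP 4.4.2.3 so that it applies to quantifiable concentrations before the first administration, that is, the Cycle 1 Day 1 pre-dose sample. Such a value, once set to missing, becomes zero under SAP 4.4.2.1; say so if that is intended.

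Add that pre-dose samples at all later visits are retained as troughs, and that the 24-hour samples of the Cycle 1 Day 1 and Cycle 3 Day 1 profiles are retained as the end points of those profiles.

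Add a rule for a Cycle 3 Day 1 pre-dose value that is missing for any reason: either how it is filled in, or that AUCss, CLss/F and RAC(AUC) are not reported for that patient.

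The cost is a few lines in the SAP. No new samples or data are needed.

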4.5 Exploratory Endpoints

4.5.1 EQ-5D-5L

The EQ-5D-5L index comprises 5 dimensions of health (mobility, self-care, usual activities, pain/discomfort and anxiety/depression). For each dimension, respondent select which statement best describes their health on that day from a possible 5 options of increasing levels of severity (no problems, slight problems, moderate problems, severe problems and unable problems). A unique EQ-5D health state is referred to by a 5-digit code allowing for a total of 3125 health states. For example, state 11111 indicates no problems on any of the 5 dimensions. These data will be converted into a weighted health state index by applying scores from the EQ5D value sets elicited from general population samples. The base case will be the United State valuation set, with other country value sets applied when needed.

In addition to the descriptive system, respondents also assess their health on the day of assessment on a visual analogue scale, ranging from 0 (worst imaginable health) to 100 (best imaginable health).

4.5.2 PRO-CTCAE

To date, The PRO-CTCAE Item Library includes 124 items representing 78 symptomatic toxicities drawn from the CTCAE. PRO-CTCAE items evaluate the symptom attributes of frequency, severity, interference, amount, presence/absence. Each symptomatic AE is assessed by 1-3 attributes.

Patients will be asked to complete those items which are considered relevant to TEAEs observed in this study, i.e. Rash, skin dryness, acne, itching, nail loss, nail ridging, decrease appetite, nausea, vomiting, diarrhea and etc. More details can be found in the protocol.

